Target	
RNOH Anaesthetic MDT: Approximately 20 staff taking part in MDT meeting taking part in the MDT meeting preparation and discussion. We aim to collect data for approximately 40 cases discussed without the Salutare One Referral software and approximately 40 patients discussed with Salutare One Referral.
 
Royal Free (Colorectal Cancer): Approximately 20 staff taking part in MDT meeting taking part in the MDT meeting preparation and discussion. We aim to collect data for approximately 120 cases discussed without the Salutare One Referral software and approximately 120 cases discussed with Salutare One Referral.
 
Royal Free (Breast Cancer): Approximately 50 staff taking part in the MDT meeting preparation and discussion. We aim to collect data for approximately 150 cases discussed without the Salutare One Referral software and 150 patients discussed with Salutare One Referral. (Note: The Royal Free Breast Cancer MDT testing is currently on hold, subject further discussions).
	
Inclusion criteria (Active Study Group)	MDT meeting Panel Members, Coordinators and staff submitting MDT referrals will take part in this study.	
Exclusion criteria (Main study)	MDT meeting Panel Members, Coordinators and staff submitting MDT referrals who are unwilling or unable to take part in the study.	
Duration of study	
The study consists of 4 phases:
 
 1. Pre-intervention period (before-study control) with no access to the Salutare One Referral software. 2. Onboarding period to allow for software installation and staff training and adjustment to the technology 3. Salutare One Referral intervention period 4. Post-intervention period (after-study control) with no access to the Salutare One Referral software 
The total duration of the study will depend on the frequency of MDT meetings and the number of cases discussed.
	

	
 • Stanmore Anaesthetics MDT and Royal Free Colorectal Cancer MDT: The study duration will be approximately 18 weeks (4-week pre-intervention period, 2-week onboarding period, 8-week intervention period, 4-week post-intervention period) • Royal Free Breast Cancer MDT: The study duration will be approximately 10 weeks (2-week pre-intervention period, 2-week onboarding period, 4-week intervention period, and a 2-week post-intervention period). 
Additionally, 4 weeks are allowed to complete the study data collection.

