The RNOH Orthopaedic MDT meets every two weeks, with approximately 10-11 participants, including Anaesthetists, General Physicians, Medical Consultants, Rehabilitation Specialists, Cardiologists, and as needed, Orthopaedic Surgeons, Pharmacists, Haematologists and Radiologists. The MDT is chaired by [name], Consultant Anaesthetist, the study Principal Investigator. The MDT focuses on discussing complex surgery cases referred by Consultant Anaesthetists, primarily for cancer (e.g. sarcoma) and cardiovascular disease. Each case undergoes team discussion facilitated by a pre-assessment document.

At present, the MDT operates without specialised software, relying on completed documents uploaded to a Shared Drive. Typically, Consultants submitting referrals will circulate a Power Point slide deck, explaining the case being reviewed. A standard form is also completed and submitted. Administrative responsibilities are shared between a

Title: Salutare Dialogue for MDTs					
Authors	[name], [name], [name]	Ver.2		Date Authorised	22/01/2025

Registrar and the MDT Chair due to the absence of an MDT administrator. A notable time-consuming task involves soliciting comments from various specialists, such as Cardiologists, to ensure thorough evaluation of the patient. The MDT typically addresses a maximum of 10 complex cases per session. Approximately 20% of cases necessitate re-presentation due to missing critical information, such as comorbidities and medication, resulting in delays in patient pre-operative pathways.

Royal Free Colorectal Cancer MDT

The Royal Free Colorectal Cancer MDT convenes weekly, reviewing approximately 30 cases. The team comprises MDT Coordinators, Colorectal Surgeons, Oncologists, Radiologists, Pathologists and Clinical Nurse Specialists. The MDT focuses on discussing complex colorectal cancer cases and findings from surgical procedures, with approximately 50% of cases presented post-surgery. Each case discussion averages 10 minutes, with surgeons typically attending in person. Case submissions are managed through a combined effort between MDT Coordinators and Surgeons.

At present, the MDT operates using paper-based documentation. Cases are recorded on standardized forms, with referrals managed jointly by Consultants and the MDT Coordinator. Cases require comprehensive documentation of imaging, pathology, and clinical findings to enable effective team discussion and treatment planning.

Royal Free Breast Cancer MDT

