8.9 Exclusion criteria

There are no formal exclusion criteria.

9. Approaching participants to join the study

MDT panel members will be invited to participate in the study through their respective Principal Investigators, who act as the MDT chairs. A notification will be sent outlining the study's purpose and the One Referral intervention. While the effectiveness of this study relies on strong participation across the entire MDT, we acknowledge the importance of individual choice and informed consent. Therefore, each MDT member will be asked to provide individual informed consent to participate in the study. This approach ensures that ethical standards are maintained while also recognizing the collaborative nature of MDT work.

MDT members will be provided with a Participant Information Sheet detailing the study's objectives, procedures, potential risks and benefits, and their rights as research participants. They will also receive a Consent Form to document their informed agreement to participate.

Patient consent for the use of their data in the One Referral system, both for the purpose of the clinical treatment and for the research study will not be sought.

Clinical treatment: Personal data processing falls under the common law duty of confidentiality. When patients consent to investigation and treatment, this implies consent for care providers to process relevant information to facilitate their referral. Research study: No patient identifiable data will be accessed by external researchers.

Title: Salutare Dialogue for MDTs					
Authors	[name], [name], [name]	Ver.2		Date Authorised	22/01/2025

Internal NHS staff will observe MDT meetings to collect data on the MDT review duration, quality and outcomes. This data will be pseudonymized by NHS researchers.

10. Study Phases

The duration of each study phase is designed to align with the frequency of Multi-Disciplinary Team (MDT) meetings. This design ensures that an adequate number of MDT meetings are observed in each phase of the study. It is important to note that this study duration is indicative and may be subject to adjustment based on operational factors. For instance, if an MDT meeting is cancelled or rescheduled, the study period might be extended to ensure the target number of MDT meetings is observed in each phase. This flexibility in the study design allows for adaptation to the real-world clinical environment while maintaining the integrity of the research protocol.

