Where possible and informative, we will provide both time-series and aggregate data. For instance, while the percentage of re-presented cases will be reported as an aggregate figure, we may also track the absolute number of re-presentations per MDT meeting as a time series to identify any trends. This multi-faceted approach to data reporting significantly strengthens the study design and allows for a more comprehensive evaluation of the Salutare One Referral software's impact. By incorporating time-series data where applicable, we observe learning effects, showing how users' proficiency evolves throughout the intervention period, while also allowing us to detect any fatigue effects or declining engagement over time. Regular data collection helps us assess the Hawthorne effect, determining whether participants' behaviour changes due to being observed and if this effect diminishes. Furthermore, the post-intervention phase data will reveal any carryover effects, indicating whether the software's impact persists after its use is discontinued (Friedman, Wyatt & Ash, 2022).

Title: Salutare Dialogue for MDTs					
Authors	[name], [name], [name]	Ver.2		Date Authorised	22/01/2025

13. Schedule of interventions and assessments

Complex case MDTs (Stanmore Anaesthetics and Royal Free Colorectal Cancer)

	Day 0	Day 1 - 28	Day 29 - 42	Day 42	Day 43 - 98	Day 98	Day 99 - 126	Day 126
Baseline survey	x							
Pre-intervention period		x						
Onboarding period			x					
Onboarding survey				x				
Intervention period					x			
Intervention survey						x		
Post-intervention period							x	
Post-intervention survey								x

High-volume MDTs (Breast Cancer)

	Day 0	Day 1 - 14	Day 15 - 28	Day 28	Day 29 - 56	Day 56	Day 57 - 70	Day 70
Baseline survey	x							
Pre-intervention period		x						
Onboarding period			x					
Onboarding survey				x				
Intervention period					x			
Intervention survey						x		
Post-intervention period							x	
Post-intervention survey								x

High-volume MDTs (Breast Cancer)

	Day 0	Day 1 - 14	Day 15 - 28	Day 28	Day 29 - 56	Day 56	Day 57 - 70	Day 70
Baseline survey	x							

Pre-intervention period		x						
Onboarding period			x					
Onboarding survey				x				
Intervention period					x			
Intervention survey						x		
Post-intervention period							x	
Post-intervention survey								x

14. Study duration

The total duration of the study will depend on the frequency of MDT meetings and the number of cases discussed.

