- Stanmore Anaesthetics MDT and Royal Free Colorectal Cancer MDT: The study duration will be approximately 18 weeks (4-week pre-intervention period, 2-week onboarding period, 8-week intervention period, 4-week post-intervention period)
- Royal Free Breast Cancer MDT: The study duration will be approximately 10 weeks (2-week pre-intervention period, 2-week onboarding period, 4-week intervention period, and a 2-week post-intervention period).

Additionally, 4 weeks are allowed to complete the study data collection.

15. Early Discontinuation/Withdrawal of Participants

This protocol ensures adherence to ethical considerations while respecting the operational dynamics of the study involving multidisciplinary teams, in accordance with UK Health Research Authority guidelines. Given that the collective participation of the whole MDT panel is required for the study to proceed, participants cannot withdraw individually without providing a reason. Therefore, a collective decision by the MDT is needed to pause or terminate the study, ensuring that the integrity and continuity of the research are maintained.

Study participants will be encouraged to contact the study team with any issues and questions and if they wish to opt out. All efforts will be made to resolve any issues. In the unlikely situation that issues cannot be resolved, the research team will discuss appropriate measures, such as allowing the panel members to submit referrals using the existing process.

Participants whose employment at the Participating Organisation is terminated during the study will be automatically withdrawn effective from their last day of employment, with no further data collected after employment ends or after the closure of their email account, whichever occurs first.

Title: Salutare Dialogue for MDTs								
Authors	[name], [name], [name]	Ver.2		Date Authorised	22/01/2025		Page 23 of 32	

While every effort has been made to ensure the safety and efficacy of the Salutare One Referral software, it is important to outline potential adverse events that might necessitate early termination of the study. The MDT panel, in consultation with the study team, may discuss early study termination if any of the following events occur:

- Cybersecurity Incidents: Any breach or attempted breach of the system that compromises or potentially compromises patient data or system integrity.

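### Section 12 says the data can show whether staff behave differently because they are observed, but no site has an unobserved meeting; intervention-phase drift is a net trend only, and at RNOH too imprecise to interpret

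*Protocol*

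**What the plan says.** Section 12 plans per-meeting time series for users engaging with the system, preparation time, per-patient discussion time and total meeting time, and says that this materially strengthens the design. It states that learning will be seen over the intervention period, and describes the series as "allowing us to detect any fatigue effects or declining engagement over time". It adds that "Regular data collection helps us assess the Hawthorne effect", including whether being watched changes behaviour and whether that change fades. Post-intervention data are to show carry-over.

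The rest of the protocol fixes what these series will contain:

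- Section 9: "Internal NHS staff will observe MDT meetings to collect data on the MDT review duration, quality and outcomes". Each panel member is told of the study and consents individually.
- Section 10 plans for meetings to be observed in every phase. Sections 10.1 and 10.4 make both control phases prospective. Section 16.6 allows observation in person or from transcripts.
- Section 6: "The RNOH Orthopaedic MDT meets every two weeks, with approximately 10-11 participants". The colorectal MDT meets weekly.
- Section 14, for both of these MDTs: "4-week pre-intervention period, 2-week onboarding period, 8-week intervention period, 4-week post-intervention period".

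**The concern.** In a before-and-after study without a concurrent control, the obvious objections are that a change reflects time, or being studied, rather than the software. Section 12 reads as the answer to those objections. If the data cannot supply it, a drift during the intervention could be reported as learning, or a flat series as reassurance about observation effects, with no support for either. The attribution is also used elsewhere: section 15 lists longer sessions or extra workload not explained by a learning curve among the events that may prompt discussion of ending the study early.

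This is not detail that an analysis plan could add later. To estimate an effect of observation, some meetings must differ in whether they are observed, and the design collects none.

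**Working it through.** **1. Meetings per phase** (phase weeks divided by weeks between meetings)

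- RNOH: 4/2, 8/2, 4/2 = 2, 4, 2.
- Colorectal: 4/1, 8/1, 4/1 = 4, 8, 4.

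The protocol states no meeting counts, but the RNOH case target gives a check. Section 6 says "The MDT typically addresses a maximum of 10 complex cases per session". Then (2 + 2) × 10 = 40 cases without the software and 4 × 10 = 40 with it. Section 1 states "approximately 40 cases discussed without the Salutare One Referral software and approximately 40 patients discussed with Salutare One Referral", so the counts reproduce the target at maximum caseload. I take the RNOH Orthopaedic, RNOH Anaesthetic and Stanmore Anaesthetics MDTs to be one panel.

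The colorectal target does not give the same confirmation: 8 meetings × 30 cases = 240, against about 120 stated with the software. I use 8 because section 8.5 includes all cases discussed in each phase. If only 120/30 = 4 intervention meetings were used, colorectal precision would fall to the RNOH level.

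**2. Is an observation effect identifiable?** Model a meeting outcome with an intercept, a software indicator and an observed indicator. The observed indicator is 1 at every meeting, so it duplicates the intercept: the design matrix has rank 2 with 3 columns, at RNOH and colorectal alike. Adding meetings adds rows, not rank.

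Transcript review does not supply the missing contrast. Staff are informed and consented whichever way a meeting is observed, and no comparison of the two modes is described.

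**3. Can learning, fatigue and fading observation be separated?** Within the intervention phase, with linear forms, the expected outcome at meeting t is a + (L + F + H)t. Four parameters meet a matrix of rank 2, so only the sum L + F + H can be estimated. Separating the terms would require assumed curve shapes.

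**4. How precisely can the net trend be estimated?** For n equally spaced meetings, Sxx = n(n² − 1)/12. In units of the between-meeting residual SD, the slope SE is 1/√Sxx. The half-width across the phase is t(0.975, n − 2) × SE × (n − 1). The 5% level and independence between meetings are my assumptions; the protocol gives no SD.

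| Series | n | Sxx | df | t | SE | Half-width per meeting | Half-width across phase |
|---|---|---|---|---|---|---|---|
| RNOH, each control phase | 2 | 0.5 | 0 | none | none | none | none |
| RNOH intervention | 4 | 5 | 2 | 4.303 | 0.447 | 1.92 | 1.92 × 3 = 5.8 |
| Colorectal, each control phase | 4 | 5 | 2 | 4.303 | 0.447 | 1.92 | 5.8 |
| Colorectal intervention | 8 | 42 | 6 | 2.447 | 0.154 | 0.378 | 0.378 × 7 = 2.6 |

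A half-width measures precision and is not a detection limit. From the noncentral t distribution, 80% power needs a true drift across the intervention phase of about 7.6 SDs at RNOH and 3.6 SDs at colorectal. For a drift of 2 SDs, power is about 15% and 35%.

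**The case against.** The strongest reply is that section 12 promises little. Section 8.5 makes the analysis descriptive, sections 8.3 and 8.6 call the study a pilot not powered for health or secondary outcomes, and section 12 is hedged. No slope test is stated, and without an SD nobody can say what 5.8 SDs means in minutes. That stands against treating the precision figures as a failed test. They serve only to show how little an RNOH slope could support. The hedging does not rescue the observation claim, because a descriptive analysis also needs something unobserved to compare with.

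Up to 10 cases per RNOH meeting add information on per-patient discussion time. They make each meeting's average more precise, but a trend over meetings still rests on four points in time. The extension rule in section 10 only makes up meetings that were cancelled or moved.

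Several stronger readings are tempting and are not supported:

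- **That the whole design lacks every property section 12 lists.** The 2/4/2 counts belong to RNOH; colorectal has 4/8/4 and can show a large net trend.
- **That carry-over cannot be examined.** It is a comparison of phase levels, so slope degrees of freedom do not bear on it.
- **That declining engagement cannot be seen.** Users, comments and referrals are counted directly and can be plotted.
- **That fading observation is confused with software learning throughout.** This holds only while the software is in use. A pre-intervention trend cannot be software learning, although it remains open to background drift and rests on two meetings at RNOH and four at colorectal.
- **That conclusions will be misreported.** The protocol nowhere says a flat series would count as proof of no observation effect; the risk is one of interpretation.

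**Conclusion.** The point holds in a limited form. The claim to establish whether being watched changes behaviour fails at every site, because all phases are observed. This needs no assumption about variance or sample size.

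For learning and fatigue, the intervention series gives one net trend. At RNOH its 95% half-width is about 5.8 between-meeting SDs over four meetings, too wide to interpret. At colorectal it is about 2.6 SDs over eight meetings, so only a large net change would stand out. These figures rest on equally spaced, independent meetings, a 5% level and the planned counts; positive correlation between successive meetings would generally widen them. The breast MDT is on hold; if it proceeds, weekly meetings over 2, 4 and 2 weeks give the same 2/4/2 counts as RNOH.

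The issue is minor: it concerns what the study may conclude from its series, not whether the series should be collected.

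**What to change.** Revise section 12 as follows:

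1. Delete the claim that the data will establish whether behaviour changes because of observation. List observation effects as a limitation that this design cannot assess at any site.
2. State that the RNOH series is a descriptive plot from which no conclusion about learning or fatigue will be drawn. Apply the same to the breast MDT if it is activated.
3. Report colorectal trends as net trends with confidence intervals, not attributed to learning, fatigue or observation.
4. Keep the descriptive engagement counts and the phase-level carry-over comparison.

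The cost is a few sentences, with no new data or visits. I do not propose building an unobserved baseline from records before Day 0. The protocol describes record access mainly for filling gaps in study data and makes both control phases prospective, so such an extraction is not shown to fall within the described scope. Dates and form completeness would also say nothing about observation effects on discussion or meeting time.

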7.3 Secondary objectives

Determination of the following metrics with and without the use of the Salutare One Referral software:

Title: Salutare Dialogue for MDTs					
Authors	[name], [name], [name]	Ver.2		Date Authorised	22/01/2025

- (1) MDT administration time
- (2) Completeness of pre-assessment information
- (3) Clinical engagement
- (4) Time spent by MDT panel members attending meetings
- (5) MDT performance rating
- (6) Duration of MDT per-patient discussion time
- (7) Overall time for MDT meetings
- (8) Time from referral submission to the generation of MDT definitive decisions.
- (9) Time from referral submission to the implementation of MDT recommendations (OPTIONAL)
- (10) Number and rate of cases re-presented for MDT review – breast cancer only
- (11) Drug changes to accommodate surgery or any disease optimisation advice
- (12) Presence or absence of peri-operative and post-operative complications (OPTIONAL)

8. Study Design

The study is designed as a mixed-methods prospective Before and After Study.

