11.4 Post-Study Assessment

Post-study assessment will be administered at the end of the post-study control period. The assessment will comprise the assessment of any safety, efficiency and effectiveness gains/losses associated with discontinuing the use of the Salutare One Referral Software.

12. Data collection from One Referral

KPI type	KPI collected
Engagement with One Referral	Number of users set up on One Referral
	Number of comments by users
	Number of referrals processed by MDTs

This study will employ a mixed reporting strategy to accurately represent different types of data collected throughout the study phases:

Time-Series Reporting:

Variables that can be meaningfully measured and reported for each MDT instance will be presented as a time series. This approach allows for the observation of trends over time and the potential identification of immediate and gradual effects of the Salutare One Referral software implementation. Examples include:

- Number of users engaging with the system per MDT
- MDT preparation time
- Duration of MDT per-patient discussion time
- Overall time for MDT meetings

Aggregate Reporting:

Some metrics are more appropriately reported as aggregate figures over the entire intervention period or for each study phase. Examples include:

- Percentage of cases re-presented to the MDT
- Mean or median time from referral submission to MDT decision implementation

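### Section 12 promises that the post-intervention phase will show carryover, but with no concurrent comparison the design cannot reliably tell carryover from a time trend

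*Protocol*

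**What the plan says.** The protocol gives the fourth phase two uses. In Section 1 (Duration of study) it is a control: "Post-intervention period (after-study control) with no access to the Salutare One Referral software". Section 11.4 uses the same label: "Post-study assessment will be administered at the end of the post-study control period". Section 12 then gives it a second purpose: "the post-intervention phase data will reveal any carryover effects", and so show whether the impact lasts once the software is withdrawn.

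Section 8 describes the design: "The study is designed as a mixed-methods prospective Before and After Study". No concurrent group without the software is described anywhere.

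Section 12 plans two kinds of reporting. Preparation time, per-patient discussion time and overall meeting time are to be shown meeting by meeting as time series. The percentage of cases re-presented and the time from referral to implementation are to be aggregated, over the intervention period or by phase. Both forms are to be given where possible. The same section expects learning, fatigue and a Hawthorne effect that may diminish.

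Section 8.5 calls the analysis descriptive. The one formal comparison it names, in the paragraph on the breast MDT, is pre-intervention against intervention. It names no contrast for the post-intervention phase.

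**The concern.** If the post-intervention phase differs from the pre-intervention phase, two explanations compete. The software may have left a lasting effect, or something else may have changed over the weeks between: case mix, staffing, season, or the effect of being observed. A fading Hawthorne effect is itself a time trend unrelated to the software, and Section 12 expects that it may occur. Saying that the data *will* reveal carryover assumes there is no such trend, and the protocol does not state that assumption.

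At stake is what the study may conclude. A time trend could be reported as lasting impact of the software. The results are meant to inform a protocol amendment and expansion to other sites (Section 8.1), to serve as evidence under the NICE framework (Section 16.1), and to be published or used in discussions with NHS executive bodies (Section 22).

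**Working it through.** **1. Schedule and stated case targets.** For the complex-case MDTs, Section 14 gives "4-week pre-intervention period, 2-week onboarding period, 8-week intervention period, 4-week post-intervention period". Section 6 says "The RNOH Orthopaedic MDT meets every two weeks, with approximately 10-11 participants", with at most 10 cases per session. The colorectal MDT meets weekly with about 30 cases.

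- RNOH: 2 pre, 4 intervention and 2 post meetings. With the software: 4 × 10 = 40. Without: (2 + 2) × 10 = 40. This reproduces the stated target of 40 and 40, but only if post-phase cases are pooled with pre-phase cases; the pre phase alone gives 20.
- Colorectal: 4, 8 and 4 meetings. Without: (4 + 4) × 30 = 240. With: 8 × 30 = 240. The stated target is 120 and 120, so this MDT does not confirm pooling.

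**2. Measures reported once per phase.** The Section 13 calendar for complex-case MDTs (Days 1–28, 43–98, 99–126) gives phase midpoints of Day 14.5, 70.5 and 112.5. The gaps are (70.5 − 14.5)/7 = 8 weeks and (112.5 − 14.5)/7 = 14 weeks. Let β be the software effect, γ the carryover and δ a linear drift per week.

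- Intervention minus pre = β + 8δ
- Intervention minus post = β − γ − 6δ
- Post minus pre = γ + 14δ

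The third line is the first minus the second, so it adds no information. With the baseline level there are four unknowns and three means (design matrix of rank 3), and γ cannot be separated from δ. If β = γ = 0, drift alone makes the post-minus-pre shift 14/8 = 1.75 times the intervention-minus-pre shift, which looks like an effect that fully persists.

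**3. Measures reported per meeting.** Fit a step for intervention, a step for post and a common linear drift to the meeting values, taken as independent with equal variance. In units of the between-meeting SD:

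SE(carryover) = √(1/n_pre + 1/n_post + G²/S)

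G is the gap in weeks between the pre and post midpoints, and S is the within-phase sum of squares of meeting week.

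- RNOH, assumed weeks 1, 3 | 7, 9, 11, 13 | 15, 17: G = 14, S = 2 + 20 + 2 = 24. SE = √(0.5 + 0.5 + 196/24) = 3.03. With drift assumed nil it is √1 = 1.00. The ratio is 3.03, with 4 residual df.
- Colorectal, weeks 1–4 | 7–14 | 15–18: G = 14, S = 5 + 42 + 5 = 52. SE = √(0.25 + 0.25 + 196/52) = 2.07. With drift assumed nil it is √0.5 = 0.71. The ratio is 2.92, with 12 residual df.
- Breast (on hold), with "2-week pre-intervention period, 2-week onboarding period, 4-week intervention period, and a 2-week post-intervention period": G = 8, S = 0.5 + 5 + 0.5 = 6. SE = √(1 + 64/6) = 3.42 against 1.00.

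If the intervention phase also needs its own slope for the learning that Section 12 expects, only the pre and post phases inform the drift. S falls to 4 at RNOH and 10 at colorectal, and the SEs become √(1 + 196/4) = 7.07 and √(0.5 + 196/10) = 4.48.

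**4. Illustration of the consequence.** Take colorectal discussion time, a software with no effect, and drift towards shorter discussions. Case numbers from the schedule are 120, 240 and 120. The SD (3, 5 or 7 minutes) and the drift are assumptions; cases are independent and tests are two-sided at 5%. With SD 5 and drift 0.1 minutes per week, the post-minus-pre shift is 14 × 0.1 = 1.4 minutes and its SE is 5√(2/120) = 0.645.

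| Drift (min/week), SD 5 | P(post differs from pre) | P(intervention and post both better than pre) |
|---|---|---|
| 0 | 0.05 | 0.006 |
| 0.1 | 0.58 | 0.25 |
| 0.2 | 0.99 | 0.82 |

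Over SD 3 to 7 and drift 0.05 to 0.2, the last column runs from about 0.03 to 0.997. The last column comes from 40,000 simulated studies per setting.

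**The case against.** The strongest reply is that this is one sentence of reporting rationale in a descriptive pilot. Persistence is neither the primary objective nor one of the twelve secondary ones, and Section 8.6 says the pilot is not powered to evaluate secondary outcomes comprehensively. The named formal comparison leaves the post phase out. The Post-Study Assessment also asks participants about gains or losses on discontinuing the software, which is subjective but separate evidence. All of this stands, and it makes the consequence one of interpretation rather than of a confirmatory error rate. It does not rescue a sentence that promises a result.

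A reader might also infer stronger things that the document does not support:

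- *That drift and carryover can never be separated.* This is strictly true only of phase-level measures. The planned meeting series identifies carryover if drift is linear, though poorly.
- *That a software with no effect would nearly always pass as persistent, because intervention and post would look alike.* Section 12 speaks of an impact that persists, which presupposes a change from pre to intervention. If a significant favourable change is required first, the rate with no effect and no drift cannot exceed 2.5%. The risk comes from drift.
- *That carryover dilutes the estimated software effect by a known amount.* That would need the post phase to enter the effect estimate in a stated way, and no such rule is given.
- *That calling the phase a control contradicts using it to look for carryover.* Section 1 defines the control only as a period without access. Return to baseline and persistence are two readings of the same observation.

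**Conclusion.** The claim in Section 12 is wrong as written. For phase-level measures, carryover and drift are not separable under this design, whatever an analysis plan might add. For per-meeting measures they are separable only on the assumption of linear drift, at about three times the standard error (3.03 times at RNOH, 2.92 at colorectal), and less precisely still if a learning slope is fitted. These ratios rest on the stated schedule and on independent meetings of equal variance. The false-persistence rates in the illustration rest on assumed drift and SD, so they show direction and possible range and are not estimates for this study. Whether post-phase cases count as discussed without the software remains open: RNOH's target fits pooling and colorectal's does not.

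**What to change.** In Section 12, replace the carryover sentence with: *differences between the post-intervention and pre-intervention phases may reflect carryover, time trends or both, and this design cannot reliably separate them.* Then:

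- report intervention minus pre and intervention minus post side by side, each with a confidence interval;
- label post minus pre as calendar drift and/or carryover, not separable;
- state that persistence will not be inferred from a lack of change between intervention and post, nor from a post-minus-pre difference alone;
- do not adopt a rule that calls an effect persistent when both intervention and post differ from pre in the same direction, because drift alone can satisfy it (25% and 82% in the illustration at 0.1 and 0.2 minutes per week, SD 5);
- state in the Target entry of Section 1 whether post-phase cases count among those discussed without the software.

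The cost is a few sentences and two contrasts per endpoint on data already being collected. The study gives up a persistence claim that it cannot support.
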